RESEARCH PROTOCOL

Date	3/1/17
Title	Impact of diet on functional gastrointestinal symptoms; a national population based survey
Principal Investigator	[name]
Sub-Investigators	[name]
Research Specialist	[name], MS
Department	Department of OB/Gyn, Division of Urogynecology and Reconstructive Pelvic Surgery; TriHealth Digestive Institute, Division of Gastroenterology
Hatton #	17-006

Purpose of Study:

- To delineate the role of diet in functional gastrointestinal (GI) symptoms.
- To determine the prevalence of functional GI disorders in the general population.
 - **Primary Aim:** To describe common triggers for food-related GI symptoms.
 - **Secondary Aims:** To assess prevalence of self-reported functional GI disorders and awareness of dietary modification programs for GI symptoms.

Hypothesis or Research Question

- We hypothesize that functional GI symptoms are very common, and may not be associated with formal diagnoses.
- We further hypothesize that certain foods may be triggers for symptoms, and that food ‘sensitivity’ is common in the population.
- Finally, we hypothesize that the majority of people are aware of gluten-free eating but are less aware of other dietary treatments for GI symptoms.

Background

Hippocrates said “Let food be thy medicine, and medicine be thy food”¹. This quote rings true today, more than ever before. Functional GI disorders, involving symptoms such as gas/bloating, diarrhea, constipation and abdominal pain, are estimated to impact between 35 and 45 million Americans, an overwhelming 15-20% of the population. These symptoms are responsible for upwards of 20 billion dollars in healthcare costs and extensive loss of quality of life for sufferers^{2,3}. Moreover, many patients suffer in silence, with 67% of subjects waiting more than a year before treatment, and 11% waiting over 10 years⁴. Irritable bowel syndrome or IBS is the most prevalent functional GI disorder⁵, and several recent studies support the idea that dietary modifications may be key to alleviating this condition⁶⁻¹⁶.

Food sensitivities and reported intolerance to lactose, gluten, wheat, and carbohydrates are increasing globally. While the mechanism is unclear, restriction of particular foods or food groups may alleviate functional GI symptoms. Indeed, both gluten-free and low-FODMAP diets

have been shown to reduce symptoms in affected patients, and not exclusively in those with celiac disease or lactose intolerance^{16,17}.

The low-FODMAP diet was initially described in 2006, and to date, dozens of well-designed studies have confirmed its benefit for IBS^{11,13-15,18-27}. FODMAP is an acronym standing for Fermentable, Oligo, Di, and Mono-saccharides and Polyols. These short-chain carbohydrates are poorly digested and can lead to symptoms of gas, bloating, diarrhea and constipation. Other disorders showing benefit from FODMAP restriction include inflammatory bowel disorders (Crohn's disease and colitis), gastroparesis, diverticulitis, post-gastric resection and small intestinal bacterial overgrowth (SIBO)^{9,12,28-32}. Benefit from this eating plan has surpassed touted success of medications commonly prescribed for IBS, without the side effects and high cost¹.

Thus, the purpose of this study is to document GI symptoms among the US population, as well as to ascertain awareness and utilization of dietary treatments that exist. Similar research has been conducted on small samples sizes in the United Kingdom¹⁷ but is lacking in the US. This information is important in identifying knowledge gaps and will aid both physicians and dietitians to educate their patients about these programs. Furthermore it is important for health care providers to understand the a priori knowledge and utilization of dietary modifications amongst sufferers of functional GI disorders.

Research Plan

- **Study Design**
 - This cross-sectional survey study will be administered through a secure online server at SurveyMonkey®.
- **Participants**
 - The survey will be administered to men and women between the ages of 18 and 80.
 - Subjects will be recruited via email.
 - A cover email will explain how to access the survey and that participation is voluntary.
 - Email addresses will be obtained through SurveyMonkey®.
 - The investigators will not have access to the email addresses or the subject contact information.
 - **Exclusion Criteria:**
 - Visual impairment.
 - Inability to read.
 - Inability to understand English.
 - Inability to use a computer to respond to questions.
- **Data Collection**
 - The survey consists of questions regarding GI symptoms³³, strategies for managing symptoms, foods that may trigger symptoms, and awareness of dietary plans for GI symptoms.
 - Demographic information will also be obtained.

- The survey instrument is attached.
- **Intervention or experimental aspect of the study**
 - There is no intervention.
- **Statistical Analysis**
 - Demographic data will be described using frequency (percentage) for categorical variables and mean (standard deviation) or median (interquartile range) for continuous variables.
 - Categorical data will be analyzed using Pearson's chi-square or Fisher's exact test; continuous data will be analyzed using Student's t-test.
 - A goal of greater than 500 subjects is sought. Sufficient emails will be obtained from SurveyMonkey® to accomplish this sample size.

Ethical Considerations

- **Informed consent**
 - By completing the survey, providers will be giving their consent to participate. No separate informed consent will be administered.
- **Privacy information**
 - The surveys are completely confidential. No identifying information will be obtained.

Cost/Budget

- Approximately \$3500 for the use of the email addresses.

Estimated Period of Time to Complete Study	
When will study begin?	2/1/2017
Protocol Development Completed	2 weeks
Admin Review Time	2 weeks
IRB Approval	3 weeks
Data collection	8 weeks
Data analysis	4 weeks
Presentation development (if applicable)	N/A
Manuscript Development (if applicable)	4 weeks
Journal submission process (if applicable)	6 months
Study closure	2 months

References

1. Chey WD. Food: The Main Course to Wellness and Illness in Patients With Irritable Bowel Syndrome. *The American journal of gastroenterology*. 2016.
4. Association AG. IBS in America Survey. 2015.
5. Saha L. Irritable bowel syndrome: pathogenesis, diagnosis, treatment, and evidence-based medicine. *World journal of gastroenterology : WJG*. 2014;20(22):6759-6773.
6. Wong WM. Restriction of FODMAP in the management of bloating in irritable bowel syndrome. *Singapore medical journal*. 2016;57(9):476-484.

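### The prevalence aim claims national population inference that a voluntary emailed survey, with no stated selection method, participation rate, interval, weighting or limit on inference, does not support

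*Combined protocol and SAP*

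**What the plan says.** Three places in the combined protocol and SAP set a population target:

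- Title: "Impact of diet on functional gastrointestinal symptoms; a national population based survey".
- Purpose of Study: "To determine the prevalence of functional GI disorders in the general population".
- Background: "the purpose of this study is to document GI symptoms among the US population".

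The secondary aim is worded more narrowly. It refers to self-reported disorders and names no population.

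The Participants section describes the source of the sample. Men and women aged 18 to 80 are recruited by email. "Email addresses will be obtained through SurveyMonkey", and the investigators see neither the addresses nor the contact details. "A cover email will explain how to access the survey and that participation is voluntary". The exclusions are visual impairment, inability to read, inability to understand English, and "Inability to use a computer to respond to questions".

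Under Data Collection, "Demographic information will also be obtained". The Statistical Analysis section says how these data will be described and gives them no other use. It then names chi-square or Fisher tests and t-tests, sets a goal of more than 500 subjects, and says that enough emails will be obtained to reach it.

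**The concern.** Prevalence in the general population is a statement about level, and so is the hypothesis that functional GI symptoms are very common. An estimate of level depends on who is counted. Here that is settled by the vendor's list, by the exclusions, and by each recipient's decision to answer. The plan describes none of these steps well enough for a reader to judge how far respondents resemble US adults, and it does not limit the claim to match. The one numerical target, more than 500 subjects, bears on sampling error and not on selection.

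The risk is that an unweighted proportion among volunteers is reported as national prevalence, with no denominator to show how many of those invited declined. If people with a disorder answer more readily, the error favours the hypothesis. If they answer less readily, it runs the other way.

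**Working it through.** **Claim against design.** The goal of more than 500 comes with no precision, power or participation rate, so there is no calculation to reproduce. The textual comparison is:

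| Needed for a population claim | In the plan |
|---|---|
| How addresses are selected | Not stated; obtained through the vendor |
| Participation denominator | Not stated; emails sufficient to reach the goal |
| Interval for prevalence | Not stated |
| Weighting or comparison with the US population | Not stated; demographics are described only |
| Stated limit on inference | None |

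**Scale (illustration only).** Inputs from the documents: n = 500, the sample size goal; and p = 15% or 20%, from the Background's "an overwhelming 15-20% of the population". Assumed input: r, the probability of responding among people with a disorder divided by that among people without. The documents give no value for r.

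1. Sampling half-width: 1.96 × sqrt(p(1−p)/n).
   - p = 0.15: 1.96 × sqrt(0.1275/500) = 3.13 points.
   - p = 0.20: 1.96 × sqrt(0.16/500) = 3.51 points.

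2. Expected proportion among responders: q = pr/(pr + 1 − p). Bias is q − p.
   - r = 1.1: 0.165/1.015 = 16.26%, bias +1.26 points; 0.22/1.02 = 21.57%, bias +1.57 points. Both are inside the half-width.
   - r = 1.5: 0.225/1.075 = 20.93%, bias +5.93 points; 0.30/1.10 = 27.27%, bias +7.27 points.
   - r = 0.75: 0.1125/0.9625 = 11.69%, bias −3.31 points; 0.15/0.95 = 15.79%, bias −4.21 points.

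3. The r at which bias equals the half-width: r = q(1−p)/(p(1−q)), with q = p ± half-width.
   - p = 0.15, up: 0.1813 × 0.85/(0.15 × 0.8187) = 1.255. Down, with q = 0.1187: 0.763.
   - p = 0.20, up: 0.2351 × 0.80/(0.20 × 0.7649) = 1.229. Down, with q = 0.1649: 0.790.

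4. Larger sample. At n = 1000 the half-widths are 2.21 and 2.48 points, while the biases in step 2 do not change. The thresholds move closer to 1: 1.178 and 1.160 upward, 0.831 and 0.850 downward. Exact coverage of a Wilson 95% interval at r = 1.25 falls from 51% and 44% at n = 500 to 25% and 16% at n = 1000 (p = 15% and 20% respectively).

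**The case against.** The strongest case on the other side has three parts.

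- Prevalence is secondary, is already worded as self-reported, and the aim itself names no population. This stands as a limit on the weight of the point, but the title, a stated purpose and the Background still make the population claim.
- The vendor may draw a random or balanced set of addresses. The documents do not exclude it. A reader might infer that this is not a probability sample, but that depends on a selection method that is not described. Voluntary response remains an issue however the addresses are drawn.
- Every figure above other than the half-widths rests on an assumed response ratio. This also stands. At r = 1.1 the bias lies within sampling error, and the 15-20% is a background estimate for functional GI disorders rather than for the self-reported outcome.

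Other stronger readings go beyond the text. A reader might infer that prevalence will be overstated, but nothing in the documents fixes the direction. A reader might infer that addresses are bought until 500 people have answered, but the plan says only that enough emails will be obtained. A reader might suppose that the cover email advertises the GI topic, but its text is not supplied. Nor does this point reach the primary aim on food triggers, or the awareness aim.

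**Conclusion.** The point holds for the secondary prevalence aim. The title, purpose and Background claim population inference, and neither the design nor the analysis section supports it. This rests on the text alone and not on any value of r.

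The size of the consequence is unknown. At 500 respondents and 15-20% prevalence, a response ratio about a quarter away from 1 (1.23-1.26 upward or 0.76-0.79 downward) would produce a bias as large as the 3.1-3.5 point half-width, and recruiting more people would not reduce it. That shows scale and is not evidence that bias is present. A reader might also infer that participation counts or a sensitivity table would recover the true prevalence. They would not, because r is not identified by anything the survey collects. This should be fixed, and the remedy is mainly to state the claim honestly and report who took part.

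**What to change.** 1. Reword the title and purpose, for example: *a national online survey of volunteer respondents*, and *to estimate the prevalence of self-reported functional GI disorders among English-reading, computer-using adults aged 18-80 who respond to an emailed survey*. State that generalisation to the US population is limited by voluntary response.
2. State how the vendor selects addresses. Before fielding, ask the vendor for the counts of invitations, starts and completes, and report participation. The investigators have no access to the addresses or contact details, so the request has to go to the vendor.
3. Make the unweighted prevalence with a Wilson 95% interval the main estimate. If age and sex are collected, add a secondary estimate post-stratified to joint US Census age-by-sex cells for ages 18-80, with prespecified age bands and a design-based interval. State that this corrects demographic imbalance only, not symptom-driven response.
4. Optionally, tabulate p = q/(q + r(1−q)) over assumed r, mapping the interval limits by the same formula. Label it a sensitivity range and not a correction. For 100 of 500 observed (20.0%, Wilson interval 16.7-23.7%), it gives 25.0% (21.1-29.3) at r = 0.75, 16.7% (13.8-19.9) at r = 1.25 and 14.3% (11.8-17.2) at r = 1.5.

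The cost is wording, one data request and a few lines of code, with no extra respondents. The title becomes more modest and the weighted interval somewhat wider. For example, if an assumed 70:30 sex split is weighted to 50:50, the design effect is 0.25/0.7 + 0.25/0.3 = 1.19. The effective sample is then 500/1.19 = 420, and the half-widths go from 3.1-3.5 to 3.4-3.8 points.

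### Does the first hypothesis, that symptoms may not be associated with formal diagnoses, need rewording and an analysis of its own?

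*Combined protocol and SAP*

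**What the plan says.** Under Hypothesis or Research Question, the first of three hypotheses is: "We hypothesize that functional GI symptoms are very common, and may not be associated with formal diagnoses". No parameter, threshold or margin is given, and the clause is not explained elsewhere.

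Three other places bear on it.

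- **Background.** It gives the burden of functional GI disorders (they "are estimated to impact between 35 and 45 million Americans, an overwhelming 15-20% of the population") and adds that "many patients suffer in silence, with 67% of subjects waiting more than a year before treatment". The second figure concerns delay to treatment, not lack of a diagnosis, so it supports the undiagnosed-sufferer reading only indirectly.
- **Purpose of Study.** The primary aim is to describe food triggers. The secondary aims are the prevalence of self-reported functional GI disorders and awareness of dietary programs. All are descriptive. The undiagnosed share is not named as an aim.
- **Research Plan, Statistical Analysis.** Percentages are written down for one class of data: "Demographic data will be described using frequency (percentage) for categorical variables". The general rule is: "Categorical data will be analyzed using Pearson's chi-square or Fisher's exact test; continuous data will be analyzed using Student's t-test". On size: "A goal of greater than 500 subjects is sought", with no derivation.

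Under Data Collection, the survey is summarised as covering GI symptoms, "strategies for managing symptoms, foods that may trigger symptoms, and awareness of dietary plans for GI symptoms", plus demographics. The instrument is said to be attached but is not in the text supplied.

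**The concern.** The clause allows two claims that can be true and false in the same data:

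- **Reading A:** many people with functional GI symptoms have no formal diagnosis. This is a proportion among the symptomatic.
- **Reading B:** having symptoms and having a diagnosis are unassociated. This compares symptomatic with other respondents.

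Taken literally, the Statistical Analysis section promises percentages for demographics and a test of independence for other categorical data. Applied to symptoms by diagnosis, that test answers neither reading in full. It does not estimate the proportion in reading A. For reading B, a non-significant result does not establish absence of association.

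Two misreadings could follow. A very small p-value could be reported as contradicting the hypothesis when most sufferers are in fact undiagnosed. Or a p-value above 0.05 could be reported as showing no association when the data leave room for a sizeable one.

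**Working it through.** The plan has no figure of its own to reproduce: the goal of more than 500 comes without alpha, power, effect size or precision. What follows is illustration at N = 500.

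**Inputs.** N = 500 is from Statistical Analysis. The number symptomatic is not given. The Background's 15-20% is the prevalence of disorders; used as a stand-in it gives 500 × 0.15 = 75 and 500 × 0.20 = 100. A value of 250 is added as an assumption, since symptoms may be commoner than disorders. All diagnosis rates are assumptions.

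**Step 1: does the test carry information on reading A?** For a table with rows symptomatic/other and columns diagnosed/not, cells a, b, c, d, the uncorrected Pearson statistic is χ² = N(ad − bc)² / [(a+b)(c+d)(a+c)(b+d)]. With 100 symptomatic and 400 others:

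| Diagnosed, symptomatic vs others | Cells a, b, c, d | χ² | p | Undiagnosed among symptomatic |
|---|---|---|---|---|
| 25% vs 5% | 25, 75, 20, 380 | 500 × 8000² / (100 × 400 × 45 × 455) = 39.07 | 4e-10 | 75% |
| 25% vs 25% | 25, 75, 100, 300 | 0 (ad = bc = 7500) | 1 | 75% |
| 80% vs 80% | 80, 20, 320, 80 | 0 (ad = bc = 6400) | 1 | 20% |

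Rows 1 and 2 have the same undiagnosed share and opposite test results. Rows 2 and 3 have the same test result and very different shares. The test says nothing about reading A.

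**Step 2: can the test confirm reading B?** With 10% vs 5% diagnosed (cells 10, 90, 20, 380), χ² = 500 × 2000² / (100 × 400 × 30 × 470) = 3.55, p = 0.060 (Fisher 0.095). The ratio is 0.10 / 0.05 = 2.0. Its log standard error is √(1/10 − 1/100 + 1/20 − 1/400) = √0.1375 = 0.371, so the 95% CI is exp(0.693 ± 1.96 × 0.371), that is 0.97 to 4.1. A non-significant result here does not show absence of association.

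**Step 3: can the test refute reading B?** Exact power of the uncorrected Pearson test, by full binomial enumeration, two-sided 5%, total 500, with 5% of the others diagnosed:

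| Diagnosed among symptomatic | 75 symptomatic | 100 | 250 |
|---|---|---|---|
| 10% | 0.40 | 0.47 | 0.57 |
| 15% | 0.83 | 0.90 | 0.97 |
| 20% | 0.97 | 0.99 | >0.999 |

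A two-fold difference is often missed; a four-fold difference is missed less than 3% of the time. So the test can refute reading B, but cannot confirm it.

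**Step 4: what would reading A's own estimate look like?** With n symptomatic, p the undiagnosed share and z = 1.96, the Wilson interval is [p + z²/2n ± z√(p(1−p)/n + z²/4n²)] / (1 + z²/n). For 80/100 this is (0.8192 ± 0.0807) / 1.0384, that is 71% to 87%, a half-width of 7.8 points. For 60/75 it is 70% to 88% (9.0 points), and for 200/250 it is 75% to 84% (4.9 points). These need only the symptomatic row of the cross-tabulation and no extra respondents.

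**Step 5: does the plan prescribe the unhelpful analysis?** The Statistical Analysis sentence on categorical data is generic and names no variables. It is not linked to the first hypothesis, nor does it say that a p-value is the only output for survey items. Describing triggers and assessing prevalence cannot be done without percentages. Reading the sentence on demographics as ruling out percentages elsewhere is therefore an inference from silence in a short protocol.

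**The case for a change.** The best case for a change is that the ambiguity is real and cheap to remove. Taken word for word, the hypothesis is a claim of no association, which is what a chi-square test addresses. No aim names the undiagnosed share, and no estimate, interval or margin is written down. An analyst following the text literally could produce a p-value and draw the wrong conclusion in either direction. Because the hypothesis asserts non-association, confirmation is what it would need, and that is what the test cannot give. One sentence would close the gap at no cost in sample size.

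Most of this stands as description: the clause is loose, no estimate is written for it, and the limits of the test are as shown. What does not stand is the step from there to a fault in the plan. Reading B depends on taking an informal clause as a statement of statistical independence. It is joined to a claim that symptoms are very common, phrased permissively, and set against a Background about people who go untreated; nothing else points to independence. The test is not assigned to this question. The summary of survey topics does not mention diagnosis, but it is a summary and the instrument is not available here, so no missing question can be inferred.

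**Conclusion.** No change to the plan follows. The clause is loosely worded, and its natural meaning is that many people with functional GI symptoms have no formal diagnosis. For that meaning the answer is a proportion with an interval, which an analyst of a descriptive survey would report as a matter of course from the same table that feeds any chi-square test. No rule stated in the plan is shown to give a wrong result.

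The point is small. It concerns one clause of one hypothesis and leaves the primary aim, data collection and sample size untouched. With 75, 100 or 250 symptomatic respondents the interval would be about 9, 8 or 5 points either side at 80% undiagnosed. In writing up, a p-value for symptoms by diagnosis should not stand in for the undiagnosed share, and p above 0.05 should not be read as no association.

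The conclusion assumes that the attached instrument asks about diagnosis and lets symptomatic respondents be identified, which cannot be checked from the text supplied. The diagnosis rates, and the use of 15-20% as a guide to the number symptomatic, are assumptions for illustration. The conclusion does not depend on them.

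### The group-comparison tests named for non-demographic categorical data do not estimate the percentages that the aims ask for, and do not fit the within-respondent awareness comparison in hypothesis 3

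*Combined protocol and SAP*

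**What the plan says.** All references are to the combined protocol and SAP.

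- **Purpose of Study.** The primary aim is "To describe common triggers for food-related GI symptoms". The secondary aims are "To assess prevalence of self-reported functional GI disorders and awareness of dietary modification programs for GI symptoms".
- **Hypothesis or Research Question.** Hypothesis 1 is that "functional GI symptoms are very common, and may not be associated with formal diagnoses". Hypothesis 2 includes the statement that food sensitivity is common in the population. Hypothesis 3 is that "the majority of people are aware of gluten-free eating but are less aware of other dietary treatments for GI symptoms".
- **Statistical Analysis.** "Demographic data will be described using frequency (percentage) for categorical variables". For categorical data in general, "Categorical data will be analyzed using Pearson's chi-square or Fisher's exact test"; continuous data get a t-test. The section names no groups to compare, no estimate or interval for any aim, and no base for the trigger percentages. On size it says "A goal of greater than 500 subjects is sought", without a derivation.
- **Data Collection.** The survey covers symptoms, management strategies, trigger foods and awareness of dietary plans. The instrument is described as attached but is not part of the text reviewed here.

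**The concern.** The questions and the stated method do not match, in two ways.

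First, most of the questions are about the size of a percentage: how many name a given food, how many have a disorder, how many know of a programme. A chi-square or Fisher p-value does not answer these. A majority could be claimed from a bare sample percentage whose uncertainty includes one half. A food could look like a common or an uncommon trigger depending on a base chosen after the data are seen.

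Second, hypothesis 3 compares awareness of one programme with awareness of others. If each respondent is asked about each programme, the two percentages come from the same people. Pearson and Fisher tests treat them as coming from separate people, so both the p-value and the implied standard error can be wrong. This goes beyond missing detail, because following the plan as written could mislead.

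**Working it through.** **Inputs.** n = 500 is the floor of the recruitment goal in Statistical Analysis. That goal has no stated inputs, so there is no figure to reproduce. All awareness rates, discordant counts, trigger counts and symptomatic counts below are assumptions for illustration. Intervals are 95%, two-sided, under simple random sampling.

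**1. Matching questions to methods**

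| Question | What answers it | Stated method |
|---|---|---|
| Primary aim: triggers | Percentage per food, on a stated base | Group test |
| Secondary aims: prevalence, awareness | Percentages | Group test |
| H1: symptoms very common | Percentage | Group test |
| H1: association with diagnosis | Between-group comparison | Group test (fits) |
| H2: food sensitivity common | Percentage | Group test |
| H3: majority aware of gluten-free | Percentage against 50% | Group test |
| H3: less aware of other programmes | Within-respondent comparison, if all are asked all items | Group test (assumes independence) |

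**2. Hypothesis 3, paired comparison.** Assume 300/500 (60%) aware of gluten-free eating and 275/500 (55%) aware of another programme.

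- Pearson, treating these as two separate groups: X² = (p1 − p2)² / [p̄(1 − p̄)(2/n)] = 0.05² / (0.575 × 0.425 × 2/500) = 0.0025 / 0.0009775 = 2.56, p = 0.11. The pairing does not enter.
- McNemar: X² = (b − c)² / (b + c), where b respondents know only gluten-free and c know only the other programme. Here b − c must equal 300 − 275 = 25.
  - b = 40, c = 15: 625/55 = 11.36, p = 0.0008.
  - b = 140, c = 115: 625/255 = 2.45, p = 0.12.
- Paired difference: SE = √[(b + c) − (b − c)²/n] / n.
  - 40/15: √53.75/500 = 0.0147, so 5.0 points (2.1 to 7.9).
  - 140/115: √253.75/500 = 0.0319, so 5.0 points (−1.2 to 11.2).
- Unpaired SE: √(0.60 × 0.40/500 + 0.55 × 0.45/500) = 0.0312, so −1.1 to 11.1, whatever the pairing.

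Where most respondents give the same answer to both items, the unpaired interval is about twice as wide as it should be (0.0312/0.0147 = 2.1).

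**3. Hypothesis 3, majority.** The Wilson interval is [p + z²/(2n) ± z√(p(1 − p)/n + z²/(4n²))] / (1 + z²/n), with z = 1.96.

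- 271/500 = 54.2%: 49.8% to 58.5%.
- 272/500 = 54.4%: 50.02% to 58.7%.

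So 251 to 271 aware is a sample majority whose interval still includes 50%. The cut-off depends slightly on method: an exact (Clopper-Pearson) lower limit first passes 50% at 273.

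**4. Trigger base.** The same 60 respondents naming one food are 60/500 = 12% of all respondents (Wilson 9.4% to 15.1%), or 60/250 = 24% if 250 are symptomatic (19.1% to 29.7%). The count is unchanged and the percentage doubles.

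**5. Hypothesis 1, association clause.** Suppose 160 of 200 symptomatic respondents have no diagnosis (80%), so 40/200 = 20% are diagnosed. If 60/300 (20%) of asymptomatic respondents are diagnosed, the odds ratio is (40/160)/(60/240) = 1.0. If 3/300 (1%) are, it is (40/160)/(3/297) = 24.75. The 80% is the same in both cases, so it cannot settle association; a between-group estimate is also needed.

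**The case against.** The strongest reply is that much of this is reporting convention. Describing triggers and assessing prevalence already imply percentages, nothing in the plan forbids them, and any analyst would report them. That is largely right for the percentages alone. It does not supply an interval, a base for the trigger percentages or a rule for majority, and it does not touch the pairing problem.

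Four stronger readings might be inferred, and the documents do not support them.

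- **That the chi-square or Fisher test is wrong throughout.** It suits hypothesis 1's association clause, and removing it would leave that clause without a test.
- **That the plan leaves every denominator open.** Statistical Analysis names none, but the aims and hypotheses speak of the general population and of people at large. All respondents is therefore the natural base for prevalence and awareness. The real ambiguity is in the trigger percentages, and skip logic in the attached survey might narrow it.
- **That the awareness data are certainly paired.** This is likely from the wording of hypothesis 3, but the instrument is not available here, so the point is conditional.
- **That subgroup precision will be poor because few respondents are symptomatic.** The Background figure, "an overwhelming 15-20% of the population", describes disorders, and hypothesis 1 expects symptoms to be very common. A wider interval in a smaller subgroup is also not in itself a fault of the plan.

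It is also fair to say that intervals do not define 'very common' or 'common'. The documents give no threshold for either, so these remain descriptive judgements.

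**Conclusion.** The point holds as a mismatch between the questions and the stated method. For most of the aims and hypotheses the named tests do not give the quantity asked for. For the comparative half of hypothesis 3 they are invalid if the same respondents answer each awareness item. In the illustration, one 5-point difference has a correct p-value of 0.0008 or 0.12 depending on discordance, while Pearson returns 0.11 in both cases. A reported majority between 50.2% and 54.2% of 500 would not exclude 50%, and a trigger percentage can double with the base chosen.

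These sizes rest on assumed rates and counts, n = 500 and simple random sampling. No erroneous result has been shown. The change is worth making before data are viewed, because the trigger base and the definition of symptomatic should not be chosen afterwards.

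**What to change.** Amend Statistical Analysis as follows.

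1. **Awareness comparisons.** Where the same respondents are asked about each programme, report gluten-free against each other programme as a within-respondent difference with a 95% confidence interval. Use McNemar's test if a test is wanted, not Pearson or Fisher.
2. **Estimates for the aims.** Report each trigger, GI symptoms, self-reported functional GI disorders, food sensitivity and awareness of each programme as n/N and percentage with a 95% interval (for example Wilson). For prevalence, sensitivity and awareness, the base is all respondents who answered the item. Claim a majority only if the lower limit exceeds 50%.
3. **Triggers.** Give the percentages both among all respondents and among symptomatic respondents. Define symptomatic from the survey's items before the data are viewed.
4. **Hypothesis 1, association clause.** Keep the chi-square or Fisher test of symptoms by diagnosis, add the difference in diagnosis rates with a 95% interval, and state that a non-significant result will not be read as no association. Also report the percentage of symptomatic respondents without a diagnosis. This item depends on the attached survey asking about diagnosis, which the sponsor should confirm.

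The cost is a few sentences and trivial extra analysis, with no added respondents. The text should say that the intervals cover sampling error only, not selection or non-response among people recruited by email.
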